3.1 Trial design

In this cluster randomized controlled effectiveness trial, 42 schools in Al Mhuka district, Taiz Governorate, Yemen were randomly assigned to one of two groups: (1) Standard of care (control) group, which WFP's school feeding program involving daily distribution of high energy biscuits (n=20); and (2) School milk (intervention) group, which received the standard of care intervention with the addition of a daily drink of milk. A baseline survey was conducted prior to the start of the milk distribution in November 2023. An endline survey was conducted at the end of the school year in May 2024.

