3.5 Sample size, power, and detectable difference

Power calculations based on available clusters in targeted districts and resource availability suggested 20 clusters (schools) per intervention arm and 30 households (with index children) per cluster. The primary outcomes of the trial include the 10-food group dietary diversity score in primary school children. For this outcome, assuming an inter cluster correlation coefficient (ICC) of 0.05, a sample size of 30 children per school leads to a minimum detectable effect size (MDES) of 0.26 SDs.

4. Sample characteristics

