7.3 Effect modification testing or subgroup analysis

Effect modification will be assessed by interacting treatment assignment with the following potential effect modifiers, selected a priori: child sex (male vs female), child age (continuous, categorical for each of the following groups 6-9, 10-14, 15-18 y), caregiver age (continuous, categorical for <20, 20-29, 30-39, 40-49, etc depending on the distribution, caregiver education (any formal vs none, to increase power), and household wealth (bottom two vs top three, to increase power). Effect modification will be considered significant at p<0.10.

8. Statistical analysis

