8.1 Framework, confidence intervals and p-values

All tests will be two-sided, at 95% confidence interval and a 5% significance level unless otherwise indicated (i.e., interaction analyses). No adjustments will be made for multiple hypothesis testing (3).

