8.3 Statistical analysis plan for each hypothesis

We will a single difference model specification of the following form:

$$Y_{i1} = \beta_0 + \beta_1 T_i + \beta_2 Y_{i0} + \varepsilon_i$$

where Y_{i0} is the outcome variable at baseline, Y_{i1} is the outcome variable at endline and T_i is a dummy variable for the treatment. This (ANCOVA) estimator has been shown to provide more efficient estimates of program impact than difference-in-difference estimators when autocorrelation of outcomes is low (4). To account for c-RCT design and the level of clustering of the outcome under analysis, we will employ linear multi-level regression models. The multi-level models will use both fixed effects with dummy variables for each intervention and random effects at the school level (unit of randomisation) to take into account clustering and to estimate the standard error in an unbiased manner. Alternative fixed effect models with standard errors clustered at the school level will also be considered. Primary analyses will be unadjusted for baseline covariates. In addition to the unadjusted primary analyses, we will report adjusted estimates, conditional on the covariates described in 7.2 above. We will use linear multi-level regression models and estimate mean differences for continuous outcomes and risk differences for binary outcomes. Alternative log-binomial and log-Poisson models will be considered for binary outcomes.

The same model will be repeated with the addition of an interaction term to assess effect modification for the variables listed in 7.3 above.

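### Effect-modification tests in a school-random-effect model with no named random slope may exceed their 10% level if modifier gradients differ between schools

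*SAP*

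**What the plan says.** Section 8.3 specifies linear multi-level models for endline on treatment and the baseline outcome. They use "random effects at the school level (unit of randomisation) to take into account clustering and to estimate the standard error in an unbiased manner". The displayed equation shows neither a school term nor a modifier. The section then closes with "The same model will be repeated with the addition of an interaction term to assess effect modification for the variables listed in 7.3 above".

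Section 7.3 lists the modifiers: child sex, child age, caregiver age, caregiver education and household wealth. It sets the threshold: "Effect modification will be considered significant at p<0.10". Section 8.1 makes tests two-sided and makes no adjustment for multiplicity.

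Section 8.3 also says that fixed effect models with school-clustered standard errors will be considered as an alternative. It gives no rule for when they replace the multi-level model and does not link them to the interaction analyses.

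**The concern.** With treatment assigned to whole schools and a modifier that varies inside each school, the treatment-by-modifier term compares school-specific gradients between the two arms. The independent units for that comparison are the 42 schools. A random intercept shifts all children in a school equally, so it largely cancels out of a within-school gradient. The interaction standard error then rests mainly on child-level residual error. It answers whether the gradients could be identical in every school, whereas 7.3 asks whether milk changes the gradient.

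The two questions coincide only if schools share one gradient. If they do not, ordinary differences between schools can be reported as milk working differently by age, sex or wealth. Some variation is plausible: the restriction to ages 6-8 was dropped at enrolment (3.3), and the age bands in 7.3 now run from 6 to 18 years.

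**Working it through.** **Inputs from the SAP.** Planned size (3.5): "20 clusters (schools) per intervention arm and 30 households (with index children) per cluster". Randomised (3.1): "42 schools in Al Mhuka district, Taiz Governorate, Yemen were randomly assigned to one of two groups", with 20 in control and so 22 in intervention by subtraction. Correlation (3.5): "assuming an inter cluster correlation coefficient (ICC) of 0.05". Interaction level: 0.10, two-sided.

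**Assumptions.** Outcome SD about 1; 15 boys and 15 girls per school (3.2 says only that selection was stratified by gender); about 40/60 for wealth (bottom two vs top three quintiles); random intercept only. The between-school SD of the gradient, τ, is not given and is varied.

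**The plan's own figure.** Section 3.5 states "a minimum detectable effect size (MDES) of 0.26 SDs". Design effect = 1 + 29 × 0.05 = 2.45. SE = √[(2.45/30)(1/20 + 1/20)] = 0.0904. With 38 degrees of freedom, two-sided 5% and an assumed 80% power, (2.024 + 0.851) × 0.0904 = 0.260. This reproduces 0.26 and confirms the setting.

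**Approximate level of the interaction test.** Let m = 30, s² = 0.95, and v be the within-school variance of the modifier (0.25 for an even binary split, 1 for age in SD units).

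- True variance of a school's estimated gradient: s²/(mv) + τ².
- Variance used by the random-intercept model: about (s² + τ²v)/(mv), since the residual absorbs part of τ².
- R is the first divided by the second. Actual level = 2[1 − Φ(1.645/√R)].

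Binary modifier, τ = 0.3: (0.1267 + 0.09)/0.1297 = 1.671, level 20.3%. In the same way τ = 0.1 gives R = 1.076 and 11.3%, and τ = 0.2 gives R = 1.302 and 14.9%. For age, v is four times larger, so τ = 0.05, 0.10 and 0.15 give the same three levels.

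**Simulation with no true interaction.** ANCOVA, 20 vs 22 schools of 30, random intercept by REML, 2,500 trials per setting (Monte Carlo SE about 0.6 points). School gradients act at endline only; the baseline coefficient is 0.3.

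| Modifier | τ (outcome SD) | Actual level of the nominal 10% test |
|---|---|---|
| Sex | 0, 0.1, 0.2, 0.3 | 11.2%, 12.4%, 17.0%, 22.1% |
| Wealth | 0, 0.1, 0.2, 0.3 | 10.2%, 11.6%, 16.1%, 21.4% |
| Age, per SD | 0, 0.05, 0.10, 0.15, 0.20 | 9.4%, 12.2%, 14.2%, 23.8%, 28.7% |

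**If gradient differences already exist at baseline.** Let ρ be the child-level baseline-endline correlation. Adjusting for Y_i0 removes about ρ of a gradient that is the same at both times. That leaves (1 − ρ)τ, with residual variance (1 − ρ²)s². For age, τ = 0.15 and ρ = 0.5: slope SD 0.075, residual variance 0.7125, R = (0.02375 + 0.005625)/0.02394 = 1.227, level 13.8%. Simulation (1,500 trials per setting) agrees:

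| Setting | Same gradient, ρ = 0.5 | Same gradient, ρ = 0.7 | Gradients correlated 0.8, ρ = 0.5 |
|---|---|---|---|
| Age, τ = 0.10 | 11.0% | not run | 13.2% |
| Age, τ = 0.15 | 14.7% | 10.7% | 16.9% |
| Sex, τ = 0.3 | 13.5% | 12.1% | 16.1% |

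A further ANCOVA simulation (800 trials per setting) gave 20-22% at an age τ of 0.15 or a sex τ of 0.3 when gradients were weakly correlated over time, and 13-16% when they persisted.

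**With schools as the unit for the interaction.** In the 2,500-trial settings, school-clustered standard errors gave 9.7% to 11.7%, and a t-test on school-specific slopes (standing in for a random slope) gave 8.9% to 11.4%. In the 800-trial run the clustered version gave about 9-13%.

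**The case against.** The strongest reply has four parts.

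- **The harm is conditional.** With no gradient variation the test is at its nominal level, and for a binary modifier at τ = 0.1 the excess is one to two points. The SAP offers nothing from which to judge τ. This stands. A reader might infer that the test will reject at twice its nominal level; the documents do not support that.
- **Baseline adjustment helps.** Differences in cognition or learning gradients that come from teaching should already be present at baseline, and Y_i0 then removes part of them. This stands too, and it is why the range is wide. It helps less where the outcome is weakly correlated over time, as may be so for 24-hour diet.
- **The remedy is already named, and the text does not exclude a random slope.** Both are true, so it would be wrong to infer that the plan lacks a valid method. But the clustered standard errors are only to be considered, and repeating the same model names no slope. The text fixes the weaker choice as the default.
- **The stakes are low.** These are supplementary tests at a lenient level without multiplicity control, so some false positives are expected anyway. That lowers the priority. It also means the per-test 10% is the only error control these analyses have, so it should be what it says.

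**Conclusion.** The point holds in conditional form. Read as a random-intercept model, the interaction analysis in 8.3 gives standard errors that are too small whenever modifier gradients differ between schools. The stated reason for the school random effects, an unbiased standard error, does not then carry over to the interaction terms.

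The level is about 10% with no gradient variation. At an age-slope SD of 0.10 it is about 13-15%, or nearer 11% if each school's gradient is identical at baseline and endline. At an age-slope SD of 0.15 or a sex-gap SD of 0.3 it is about 20-24% when the differences are mostly new at endline, and about 11-17% when they persist from baseline. These figures rest on the assumed τ, the correlations over time, even school sizes of 30 and the random-intercept reading.

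A reader might extend this to the main treatment comparison. That does not follow: the school random intercept addresses clustering there, and the 0.26 SD detectable effect is reproduced and untouched. This is a cheap improvement to secondary analyses, not a threat to the trial's main conclusion.

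**What to change.** Replace the last sentence of 8.3 with wording such as: *Effect modification will be assessed by adding the modifier and its product with treatment to the model. Inference on the product term will use standard errors clustered by school, with a t reference distribution on the number of schools minus 2 degrees of freedom.* With 42 schools that is 40 degrees of freedom. A school-level random slope for the modifier would serve the same purpose; the SAP should name one of the two as the rule. Record the change in Section 9.

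The cost is one sentence and one model option, with no new data. Interaction intervals become somewhat wider when gradients differ between schools. When they do not, the standard error is slightly noisier and little else changes.

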8.5 Statistical assumptions and diagnostics

All variables will be assessed for normality using a Shapiro-Wilk test. If a variable is skewed, it will be transformed via log transformation. We will assess collinearity using pairwise Pearson correlations between all covariates. If two covariates are collinear with one another, one will be selected for inclusion in the regression.

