6.2 Outcome variable definitions

- Diet diversity score in children will be measured using the Minimum dietary diversity for women (MDD-W) guidelines at baseline and endline. We will calculate a count score, summing 10 foods groups, and a binary indicator for consuming ≥5 food groups in the previous 24h. Milk consumption will be calculated using self-reported consumption in the previous 24h.
- Cognition in children will be measured using the forward and backward digit span and the standard progressive matrices at baseline and endline. We will calculate raw scores summing the correct responses to each module. We will also calculate standardized scores, standardized within the sample. If age and sex distributions allow, we will calculate age and sex standardized scores. We will also use structural equation modeling to examine cognition as a latent construct.
- Learning in children will be measured using literacy and numeracy scores at baseline and endline. We will calculate raw scores by summing the correct responses to each set of questions. We will also calculate standardized scores, standardized within the sample. If age and sex distributions allow, we will calculate age and sex standardized scores.
- Nutritional status will be measured using body mass index Z-score (BMIZ) and height-for-age Z-score (HAZ) at baseline and endline. BMIZ and HAZ will be calculated using the WHO 2007 Growth Reference (2). Stunting will be defined as HAZ <-2. Thinness will be defined as BMIZ <-2. Overweight will be defined as BMIZ as >1 and obesity as BMIZ >2 (2).
- School attendance will be measured using school observations at baseline and endline. We will calculate the total number of students present on the day of the visit.
- Perceptions of the school feeding program will be measured using caregiver self-report at baseline and endline. Binary indicators will be created for different variables to show the proportion of caregivers with a perception.
- Child health will be measured using caregiver report of child morbidity symptoms at baseline and endline. We will create binary indicators for each symptom experienced. We will also calculate a summary indicator for the total number of symptoms experienced.

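### Section 8.5 requires a log transformation of any skewed variable, which cannot be applied to outcomes with zero or negative values and conflicts with the mean difference planned in 8.3

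*SAP*

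**What the plan says.** Section 8.5 of the SAP begins with a screen, "All variables will be assessed for normality using a Shapiro-Wilk test", and follows it with an instruction: "If a variable is skewed, it will be transformed via log transformation". The instruction is mandatory and covers outcomes and covariates alike. It gives no skewness cut-off, offset, alternative transformation or rule for reporting a transformed result.

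Section 8.3 fixes the effect measure. Linear multilevel models will "estimate mean differences for continuous outcomes and risk differences for binary outcomes". The model is an ANCOVA, "where Y_{i0} is the outcome variable at baseline, Y_{i1} is the outcome variable at endline", so the same outcome enters at both visits.

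Section 6.2 defines the outcomes to which 8.5 would apply:

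- Nutrition: "Nutritional status will be measured using body mass index Z-score (BMIZ) and height-for-age Z-score (HAZ) at baseline and endline". The plan itself expects negative values: "Stunting will be defined as HAZ <-2".
- Cognition and learning: raw sums of correct responses, and in addition "We will also calculate standardized scores, standardized within the sample".
- Diet diversity, a primary outcome under 6.3: "We will calculate a count score, summing 10 foods groups".
- Child health: a binary indicator per symptom and a total count of symptoms.

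Section 8.2 says that missing outcomes are not imputed, and 5.3 specifies intention-to-treat. Section 3.5 states the detectable effect for the diet-diversity score as 0.26 SD.

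**The concern.** The rule fails in one of two ways when it meets a skewed outcome.

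- **The log does not exist.** HAZ, BMIZ and within-sample standardized scores take negative values, and the two counts can be zero. With no offset named and no imputation of outcomes, the analyst either loses those children, a selection on the outcome that runs against intention-to-treat, or invents a constant on which the result depends.
- **The log exists but answers another question.** For a positive outcome, the coefficient on the logged scale is a log ratio of geometric means. Section 8.3 promises a mean difference, and 3.5 plans the trial in SDs of the diet-diversity score.

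The screen is also aimed at the wrong object. The linear mixed model makes assumptions about residuals and school effects. It does not need the outcome to be marginally normal, and it assumes nothing about the distribution of covariates. With no cut-off for skewness, the choice of which outcomes to log is left until the data have been seen.

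**Working it through.** **1. The plan's own figure and its scale.** Inputs from 3.5: 20 schools per arm, 30 children per school, ICC 0.05. Power is not stated; 80% is assumed, with a two-sided 5% level (8.1).

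- Design effect = 1 + (30 − 1) × 0.05 = 2.45.
- Standard error in SD units = √(2 × 2.45 / 600) = 0.0904.
- Detectable effect with 38 degrees of freedom = (2.024 + 0.851) × 0.0904 = 0.260. With normal quantiles it is 0.253.

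The stated 0.26 SD is reproduced. It is a mean difference in SD units of the untransformed score, so it does not carry over to a logged score.

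**2. How much of a skewed standardized score has no log.** A within-sample standardized score has mean 0, so the share lost is the share at or below the mean. The SAP gives no distributions; a gamma shape is assumed.

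- Right-skewed, gamma with shape 2 (skewness 1.41): P(X ≤ 2) = 1 − 3e⁻² = 0.594.
- Left-skewed, the mirror image: 1 − 0.594 = 0.406.
- Milder skewness lies between: with shape 8 (skewness 0.71), 0.547 and 0.453.

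The range is therefore about 40% to 60%.

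**3. Whether the loss depends on the arm.** Take the right-skewed gamma and a true shift of 0.26 SD. The SD is √2, so the shift is 0.26 × 1.414 = 0.368, and with equal arms the pooled mean is 2 + 0.184 = 2.184. The share kept is P(X > c) = e⁻ᶜ(1 + c).

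- Control, c = 2.184: 0.1126 × 3.184 = 0.36.
- Milk, c = 2.184 − 0.368 = 1.816: 0.1627 × 2.816 = 0.46.

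Dropping undefined values would keep 36% of one arm and 46% of the other, so the two sets would not be comparable.

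**4. What the log does to a positive count.** One extra food group is ln(4/3) = 0.29 log units from 3 groups, ln(5/4) = 0.22 from 4 and ln(6/5) = 0.18 from 5. The same gain in food groups counts for more in a child who starts low, so the logged coefficient cannot be read as a mean difference.

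**5. Zeros in the counts.** With diet scores simulated as a normal with mean 4 and SD 1.5, rounded and clipped to 0–10 (an assumption), about 1% are zero. For a symptom count assumed Poisson with mean 0.5, 1 or 2, the share of zeros is e⁻⁰·⁵ = 61%, e⁻¹ = 37% or e⁻² = 14%.

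**6. Shapiro-Wilk as a screen.** The sample is 40 × 30 = 1,200 children on the figures in 3.5, or 42 × 30 = 1,260 on the school count in 3.1 and 3.4. In 1,000 simulated samples of 1,260 of the near-symmetric diet scores from step 5, Shapiro-Wilk rejected at 5% in all 1,000. A test of skewness rejected in 49 (mean skewness 0.02, range −0.17 to 0.22); a repeat gave 40. The first test reacts to the integer scale, not to the shape.

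**The case against.** The strongest reply is that 8.5 contains two sentences and that only skewness triggers the log. Shapiro-Wilk is named as an assessment; the text does not say that its rejection leads to a transformation. That stands. A reader might infer from step 6 that the primary diet score would certainly be logged. The document does not support this: on those same scores a skewness criterion would fire in about 4% to 5% of samples.

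A reader might also infer that the rule would remove most children from the HAZ or BMIZ analysis. A normal HAZ with SD 1.1 has 50% of values at or below zero if its mean is 0, 82% at mean −1 and 91% at mean −1.5. But a normal variable is not skewed, so the rule would not normally apply to it. In 1,000 normal samples with mean −1.5, a skewness test rejected in 44, about its nominal rate. These percentages are not the effect of the rule.

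Three further points have weight. The SAP nowhere tells the analyst to exclude children, and a loss of half the sample would be noticed, so an improvised offset or a quiet departure from the plan is more likely than silent selection. For cognition and learning a raw score is also planned, and it can be logged apart from zeros. Logging a positive skewed covariate does little harm, and the primary analyses adjust for no covariate beyond the baseline outcome.

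None of this removes the defect. Where an outcome is judged skewed, every way of proceeding departs from the SAP, needs a constant that it does not give, or changes the effect measure fixed in 8.3.

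**Conclusion.** The point holds in conditional form. Section 8.5 cannot be executed as written on a skewed HAZ, BMIZ or standardized score, or on a skewed count that contains zeros. On a skewed positive outcome it contradicts 8.3 and the scale of the 0.26 SD in 3.5.

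If a standardized score is skewed, about 40% to 60% of its values have no log, under assumed gamma shapes with skewness up to 1.41. For the primary diet-diversity score the main harm is the changed effect measure; lost children are a minor matter there, with about 1% zeros under the assumed distribution. The large losses concern secondary outcomes.

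The documents do not show that any particular outcome will be skewed, and they do not support a claim that the rule will drop children in every case. This should be fixed before analysis, because the scale of the reported effects should not depend on the data. It does not call the design or the sample size into question.

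**What to change.** In section 8.5, remove the Shapiro-Wilk test and the log rule for outcomes. State that every outcome is analysed on its native scale as the main result, with the effect measures of 8.3. Limit the diagnostics to child-level and school-level residuals from the fitted models. If these look poor, report the school-clustered standard errors already named in 8.3 as a sensitivity analysis. Any analysis on a transformed scale should be labelled supplementary, with the transformation and any constant specified in advance.

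The cost is a change of SAP wording. No new data are needed, and the 0.26 SD planning figure remains applicable.
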